11.2 General Analytic Strategy

11.2.1 Significance Testing

All hypotheses will be tested by two-sided tests with level of significance $\alpha=0.05$. All exploratory analyses will be reported as such and will be thoroughly described in any publication. In particular, the modeling strategy for identification of predictors of outcome (such as inclusion of multiple covariates and interactions) will be explained in detail to allow adequate assessment of the strength of inferences based on data-driven statistical models.

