11.4.3.2 Sample size

A total of 324 subjects will be randomized in Phase 2. Participants in Phase 2 are Phase 1 treatment failures. About 50% of patients enrolled in Phase 1 are expected to be eligible, willing, and to actually enroll in Phase 2. The treatment dropout rate in Phase 2 is expected to be lower than that in Phase 1, since participants in Phase 2 have had experience with the study and have agreed to continue, and because dropout from a stabilization dose of BUP/NX is typically lower than that from a tapering dose. In Phase 2 a rate of about 5% treatment dropout per month is expected, resulting in 15% treatment dropout during the three months of treatment and total of 30% treatment dropout for the entire study (10% treatment dropout per month is expected in Phase 1, or about 30% during the three months of Phase 1).

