- b. Effect of craving on treatment outcome: The effect of craving on outcome will be studied by modeling the probability for substantial improvement as a function of treatment, and a measure representing the course of craving during treatment, and their interaction. As measures of craving during treatment, the average craving over the 12 weeks of treatment and the average craving in the last month of treatment or the patient's craving slope from model (1) above will be considered. A significant interaction effect between treatment and the measure of craving would indicate that the level of craving during the treatment period has a different effect on abstinence depending on the treatment. For instance, EMM might be equivalent to SMM among patients without craving, but might be more effective than SMM among patients with a severe course of craving. If the interaction term is not significant, a model with main effects (treatment and course of craving) will be considered and the estimated treatment effect from this model will be compared with the treatment effect estimated from model (1). If the latter is larger (in magnitude) than the former, this would indicate that the course of craving mediates treatment effect and is at least a partial mediator. If the treatment effect from the model with main effect and treatment and course of craving is not significant, this would indicate that craving is a complete mediator of treatment effect.

In addition, the association between the weekly craving and the weekly probability for negative urine will be studied. Appropriate logistic regression models with GEE method of estimation will be used to account for the correlation between the repeated weekly measures and the correlations between patients from the same site.

6. Withdrawal symptoms: the effect of the withdrawal symptoms at baseline in Phase 1 on the outcome of the treatment will be studied. In addition, the signs and symptoms of withdrawal change at the end of the taper period, and at 4- and 8-week followups, will be studied.
7. The relationship between the treatment at Phase 1 and the outcome in Phase 2: the EMM or SMM assignment in Phase 1 is not expected to affect outcome in Phase 2. However, that eventuality will be formally tested. For example, in an exploratory analysis of primary hypothesis 2.1 the following model will be fit:

(1)

$$(2) \text{logit}(Y_{it}) = \beta_0 + \beta_1 txt_{ij} + \beta_2 t I_{ij}^s + \beta_{12} I_{ij}^s txt_{ij} ,$$

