	0.40	0.55	0.15	1.36
	0.45	0.60	0.15	1.32
	0.50	0.64	0.14	1.29
1.90	0.20	0.32	0.12	1.61
	0.25	0.39	0.14	1.55
	0.30	0.45	0.15	1.50
	0.35	0.51	0.16	1.44
	0.40	0.56	0.16	1.40
	0.45	0.61	0.16	1.35
	0.50	0.66	0.16	1.31
2.00	0.20	0.33	0.13	1.67
	0.25	0.40	0.15	1.60
	0.30	0.46	0.16	1.54
	0.35	0.52	0.17	1.48
	0.40	0.57	0.17	1.43
	0.45	0.62	0.17	1.38
	0.50	0.67	0.17	1.33

Figure 11.2, page 18 shows how the P_{SMM} , odds ratio, total sample size, and correlation within site (ρ) affect the power. Here, the following assumptions were conservatively made:

- The substantial improvement rate in the SMM group is between 30% and 50%.
- The correlation for each pair of responses (substantial improvement) from the same site is about 0.1.
- Between 20 and 30 patients are recruited from each site.

Figure 11.2 Odds Ratios

Top left: Power vs. the correlation for each pair of the substantial improvement rate from the same site (ρ) given site # = 12, sample size per site = 27, $P_{SMM} = 0.30$ and odds ratio = 1.8, 1.9 and 2.0.

Top right: Power vs. P_{SMM} given site # = 12, sample size per site (Phase 2) = 27, $\rho = 0.1$ and odds ratio = 1.8, 1.9 and 2.0.

Bottom left: Total sample size vs. Power given site # = 12, $P_{SMM} = 0.30$, $\rho = 0.1$, and odds ratio = 1.8, 1.9 and 2.0.

This figure conveys at least 80% power to detect an odds ratio of 1.9 between EMM and SMM group or to detect that the difference in substantial improvement rate between two groups is greater than 16% with $324 = 12 \times 27$ total patients enrolled in Phase 2. If the conservative assumption is made that about 50% subjects enrolled in Phase 1 will actually enroll in Phase 2, then the required sample size in Phase 2 is equivalent to a total sample size 648 in Phase 1.

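### The craving mediation rule in Section 11.4.5, item 5b, reads a non-significant adjusted treatment effect as complete mediation, so a trial with no treatment effect usually receives that label

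*Protocol*

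**What the plan says.** Item 5b models substantial improvement on treatment, a summary of craving during treatment, and their interaction. The next step has one written condition: "If the interaction term is not significant, a model with main effects (treatment and course of craving) will be considered". Two interpretive rules follow.

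- **Partial mediation.** The treatment effect from the main-effects model is compared with the one from the model without craving: "If the latter is larger (in magnitude) than the former, this would indicate that the course of craving mediates treatment effect". The sentence adds that craving is then at least a partial mediator. No test of the difference and no interval are asked for.
- **Complete mediation.** "If the treatment effect from the model with main effect and treatment and course of craving is not significant", then "this would indicate that craving is a complete mediator of treatment effect".

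Item 5a, just before, tests whether treatment affects the course of craving, but item 5b does not depend on its result. Section 11.2.1 sets two-sided tests at 0.05. Section 11.4.5 opens by ranking evidence from these analyses below that from the primary and secondary objectives.

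**The concern.** The complete-mediation rule takes failure to reject as evidence that the direct effect is zero. A non-significant adjusted coefficient can arise because all of the effect passes through craving. It can equally arise because there was never an effect, or because the trial was too small to show the direct part. The rule gives all three the same label.

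The partial rule has a related fault. Two estimates from the same data will rarely coincide, so chance alone often makes the adjusted one smaller.

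At stake is the explanation attached to the trial's result. The complete-mediation label is most likely when EMM does nothing, which is when a statement that EMM works through craving would mislead most.

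**Working it through.** **Inputs from the protocol.**
- Phase 2 size: "A total of 324 subjects will be randomized in Phase 2" (Section 11.4.3.2). Equal allocation, 162 per arm, is assumed because no ratio is stated.
- Two-sided alpha of 0.05 (Section 11.2.1).
- SMM improvement rate of 30% to 50% and within-site correlation of about 0.1 (Section 11.5.3). The 30% end is used.
- Design effect: "at least 80% power to detect an odds ratio of 1.9 between EMM and SMM group" (Section 11.5.3).

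**Assumptions.** The protocol gives no effect sizes for craving. Craving is taken as a standard normal score, unaffected by treatment, so true mediation is zero. It is either unrelated to outcome or lowers the log-odds of improvement by about 0.7 to 0.8 per standard deviation. The comparison model is read as the unadjusted logistic model of Hypothesis 2.1. Models were fitted without site clustering.

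**Step 1: reproduce the stated power.** The EMM rate at odds ratio 1.9 is (1.9 × 0.30/0.70) / (1 + 1.9 × 0.30/0.70) = 0.8143/1.8143 = 0.4488, a difference of 0.1488. With power = Φ[(d − 1.96·SE₀)/SE₁]:
- SE₀ = √(0.3744 × 0.6256 × 2/162) = 0.0538
- SE₁ = √((0.30 × 0.70 + 0.4488 × 0.5512)/162) = 0.0531
- Power = Φ(0.817) = 79.3%

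Multiplying the variances by (1 − 0.1), because randomization is within site, gives 83.4%. At SMM rates of 35% to 50% the results are about 81–82% and 85–86%. The protocol's figure reproduces.

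**Step 2: the rule by hand.** With no interaction, the gate is passed about 95% of the time. If craving is also unrelated to outcome, the adjusted test behaves like the unadjusted one, so P(complete mediator) ≈ 0.95 × (1 − power).
- No effect: 0.95 × 0.95 = 0.90. This does not depend on any assumed craving effect.
- Odds ratio 1.5, simulated power 41.4%: 0.95 × 0.586 = 0.56.
- Odds ratio 1.9: 0.95 × (1 − 0.793) = 0.20.

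**Step 3: simulation of the rule, as a share of all trials.** Odds ratios are marginal, matching the unadjusted effect the protocol powers for. Ranges cover craving that does and does not predict outcome.

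| Reading of the complete-mediation rule | No effect | OR 1.5 | OR 1.9 |
|---|---|---|---|
| As written | about 90% | 52–57% | 16–20% |
| Also requires the coefficient to fall | about 42% | 19–27% | 5–10% |
| Also requires a significant total effect | about 0.2–3% across the three settings | | |

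**Step 4: can the rule tell the cases apart?** With true complete mediation (assumed shift in craving of −0.9 SD, log-odds slope −0.7, no direct effect) the rule says complete in 90% of trials, the same share as with no effect at all. With partial mediation only (direct odds ratio 1.6, shift −0.25 SD, slope −0.7) it says complete in 49%. Even the strictest reading in the table mislabels that case in 22%.

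**Step 5: the partial rule.** With no treatment effect, a chance fall in the coefficient gives the partial label in about 43% of trials. At odds ratio 1.9 the share is about 42% when craving is unrelated to outcome and about 14% when it is prognostic.

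**The case against.** The strongest reply is that the two rules are sequential. Complete mediation can be read as a step beyond partial mediation, and speaking of a mediated treatment effect may presuppose that there is one. Item 5a also examines treatment and craving immediately beforehand. With every one of these conditions in force, false claims of complete mediation under zero mediation almost disappear. But the text states none of them: its only condition is the interaction test. Requiring only the coefficient to fall still mislabels about 42% of trials with no effect.

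The second reply is that this is one of nine exploratory topics, to be reported as exploratory and given less weight. That limits the severity. It does not make the inference valid, because the protocol itself fixes what a non-significant result is taken to mean.

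Three stronger readings are tempting and are not supported:
- A reader might infer that the label is given in 95% of trials with no effect. That is the share among trials that pass the interaction test. Of all trials it is about 90%.
- A reader might infer that non-collapsibility of the odds ratio manufactures mediation. It does make the two logistic coefficients non-comparable. With craving independent of arm, however, adjustment moves the coefficient away from zero: at marginal odds ratio 1.9 and slope −0.8, the mean estimates are 0.645 unadjusted and 0.736 adjusted. It therefore tends to hide mediation, as the 14% against 42% above shows.
- A reader might infer that the trial's main findings are at risk. No primary or secondary hypothesis uses this rule.

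**Conclusion.** The point holds at low severity. As written, item 5b cannot separate no treatment effect from complete mediation: each receives the complete label in about 90% of trials. At the design effect with no mediation, the false label appears in about 16–20% of trials as written and 5–10% if the coefficient must also fall. The partial rule counts chance falls, about 43% of the time when EMM has no effect.

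The 90% figure follows from the two 5% tests alone. The other figures rest on 324 patients split equally, a 30% SMM rate, marginal odds ratios, a normally distributed craving score and no site clustering. The partial- and complete-mediation scenarios also depend on assumed craving effects that the protocol does not supply.

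**What to change.** In Section 11.4.5, item 5b:

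1. Delete the sentence that infers complete mediation from a non-significant adjusted effect, and the rule that treats any numerical fall in the coefficient as mediation.
2. Report instead an estimate of the indirect effect with a 95% confidence interval on a collapsible scale such as the risk difference. A bootstrap is one suitable method; the choice can be left to the analysis plan.
3. Interpret that estimate only if Hypothesis 2.1 shows a total effect and item 5a shows that treatment changes craving.
4. State that craving during treatment is not randomized, so confounding between craving and outcome remains and the indirect effect is not established as causal.

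The cost is a few lines of wording and slightly more analysis work. Data collection, sample size and the primary and secondary analyses do not change.

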11.3.3.2 Sample size

Approximately 648 subjects will enter Phase 1. Starting after the second week, they will be monitored for meeting the treatment failure criteria (see *Primary Outcome Measures* on page 11-5) (needle use would indicate failure prior to Week 2). At any time of meeting failure criteria, participants will be given the option to transition from Phase 1 to Phase 2. However, failures can elect to remain in Phase 1 through Week 12 follow-up and can transition to Phase 2 at any time up until the conclusion of Phase

1. Approximately 20% (average over EMM and SMM) are expected to be treatment successes, and about 30% are expected to drop out or refuse entry into Phase 2.

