where I_{ij}^S is an indicator variable, $I_{ij}^S = 1$ if the subject is in EMM at Phase 1 and $I_{ij}^S = 0$ if the subject is in SMM group at Phase 1. A significant interaction term β_{12} would indicate that the relative efficacy of EMM in Phase 2 depends on the treatment assignment in Phase 1. If β_{12} is not significantly different from 0, the data will be refit with a model without interaction term. GEE approach will be used to fit this model. Similar exploratory analysis will be performed for the secondary hypotheses.

8. Effect of time to failure and pattern of drug use in Phase 1 on the treatment outcome in Phase 2.
9. Age, gender and ethnic differences: the relationship of gender, ethnicity, and age to outcome will be explored.

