11.5.2 Phase 1: Detectable effects

The success rates for SMM and EMM is expected to be 10%-20% (P_{SMM}) and 20%~30% (P_{EMM}), respectively, and the within site correlation will be small ($0 \sim 0.1$). Table 11.1 shows the power for different combination of P_{SMM} and P_{EMM} based on Model 1. The rightmost three columns represent the percentage of subjects enrolled in Phase 1 who will be eligible for Phase 2, drop out in Phase 1 or refuse to enter in Phase 2, and actually enter in Phase 2. Assume the difference between the success

rate between SMM and EMM is about 10%. The proposed sample size (648) gives sufficient power (>80%) to detect the difference with a two-sided test at $\alpha = 0.05$.

Table 11.1 Power for detecting EMM vs. SMM effects in Phase 1 with n=648, and percent of subjects eligible for Phase 2 and percent entering Phase 2 out of the total n=648.

P_{SM} M	P_{EM} M	Difference $P_{EMM} - P_{SMM}$	Odds Ratio ^a	Power	Drop/Ref Rate Phase 1	Eligible for Phase 2 ^b	Entering Phase 2 ^c
0.1	0.15	0.05	1.59	49%	25%	88%	63%
	0.18	0.08	1.98	84%	25%	86%	61%
	0.2	0.1	2.25	95%	25%	85%	60%
0.15	0.2	0.05	1.42	39%	25%	83%	58%
	0.23	0.08	1.69	74%	25%	81%	56%
	0.25	0.1	1.89	89%	25%	80%	55%
0.2	0.25	0.05	1.33	33%	25%	78%	53%
	0.28	0.08	1.56	67%	25%	76%	51%
	0.3	0.1	1.71	84%	25%	75%	50%
0.25	0.3	0.05	1.29	30%	15%	73%	58%
	0.33	0.08	1.48	62%	15%	71%	56%
	0.35	0.1	1.62	80%	15%	70%	55%
0.3	0.35	0.05	1.26	27%	15%	68%	53%
	0.38	0.08	1.43	58%	15%	66%	51%
	0.4	0.1	1.58	80%	15%	65%	50%

a) Odds Ratio = $[P_{EMM}/(1-P_{EMM})]/[P_{SMM}/(1-P_{SMM})]$

b) Eligible for Phase 2 = 1 - overall success rate in Phase 1 = 1 - $(P_{SMM} + P_{EMM})/2$

c) Entering Rate for Phase 2 = Eligible for Phase 2 – Dropout/Refusal Rate in Phase 1.

The table shows that the sample size planned for Phase 1 affords sufficient power to detect differences in success rate between EMM and SMM as small as 10%. It also shows the range of realistic assumptions about success rate in Phase 1 and dropout (unable to locate or refusal to enter Phase 2) in Phase 1 that result in at least 50% of subjects in Phase 1 going into Phase 2.

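### Item 7 of Protocol 11.4.5 promises a formal test of whether Phase 1 assignment affects Phase 2 outcome, but fits it only among Phase 1 failures who entered Phase 2, so it can only describe an association among entrants

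*Protocol*

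**What the plan says.** Protocol 11.4.5, item 7, states that "the EMM or SMM assignment in Phase 1 is not expected to affect outcome in Phase 2. However, that eventuality will be formally tested". As an example it takes the model for Hypothesis 2.1 and adds an indicator for Phase 1 arm and its interaction with Phase 2 treatment. A significant interaction is to be read as the relative efficacy of EMM in Phase 2 depending on Phase 1 assignment. Otherwise, "the data will be refit with a model without interaction term". Similar analyses follow for the secondary hypotheses.

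The sample is fixed by Protocol 11.4.3.2: "Participants in Phase 2 are Phase 1 treatment failures". They must also have agreed to enter.

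On Phase 1, Hypothesis 1.1 (Protocol 11.3.4) expects a higher success rate on EMM, and Protocol 11.5.2 gives the rates: "The success rates for SMM and EMM is expected to be 10%-20% (P_{SMM}) and 20%~30% (P_{EMM}), respectively". Protocol 11.4.3.1 stratifies the Phase 2 randomisation by Phase 1 arm. The opening of 11.4.5 ranks its evidence below that of the primary and secondary analyses. Item 7 itself mentions neither selection nor adjustment for prognosis.

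**The concern.** Phase 1 arm was randomised among all Phase 1 subjects. Item 7 compares the arms only among those who failed and then chose to enter, and both steps come after that randomisation. At 15% vs 25% success, 85% of SMM subjects and 75% of EMM subjects remain eligible. If those removed as successes tend to have the better Phase 2 prognosis, more of the good prognosis has been removed from the EMM side. The Phase 1 arm main effect then mixes any true carry-over with a difference in who is left.

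The bias runs towards prior counselling looking harmful, and it grows with the benefit of EMM in Phase 1. It can mimic harm or hide a real benefit. Because the text promises a formal test, a reader could take the p-value as evidence about the effect of assignment.

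**Working it through.** **Inputs from the protocol.** Two-sided 5% level (11.2.1); 648 subjects in Phase 1 (11.3.3.2) and 324 in Phase 2 (11.4.3.2); Phase 1 success 10-20% on SMM and 20-30% on EMM (11.5.2); Phase 2 improvement on SMM 30-50% and a detectable difference of 16 points (11.5.3). From 11.3.3.2: "Approximately 20% (average over EMM and SMM) are expected to be treatment successes, and about 30% are expected to drop out or refuse".

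**Assumed, not in the protocol.** 1:1 allocation in Phase 1, the link between Phase 1 and Phase 2 prognosis (shown as a range), entry unrelated to arm given failure, no site clustering, and no true carry-over.

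**The plan's own figure.** A two-proportion test with 324 per arm at 15% vs 25% gives 89.1% power, against 89% in Table 11.1. Eligible for Phase 2 = 1 - (0.15 + 0.25)/2 = 80%, as stated. This row matches the expected 20% overall success, so it is used below.

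**Model A, normal latent prognosis.** Success occurs when latent prognosis exceeds the arm's (1 - P) quantile. The Phase 2 latent outcome has correlation ρ with it, and the threshold is set so that 40% of SMM failures improve. The rejection rate uses 324/2 = 162 entrants per Phase 1 arm.

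| ρ | EMM failures minus SMM failures | Share of 16 points | 5% test rejects |
|---|---|---|---|
| 0.3 | -1.8 points | 11% | 6% |
| 0.5 | -3.2 points | 20% | 9% |
| 0.7 | -4.9 points | 31% | 15% |

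Results at 10% vs 20% and at 20% vs 30% are nearly the same.

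**Model B, logistic.** A standard normal prognosis has the same log-odds slope b in both phases. Mean improvement is 38%, with 172 SMM and 152 EMM entrants (324 split in the ratio 85:75).

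| b | Spurious difference | Odds ratio | 5% test rejects |
|---|---|---|---|
| 0.5 | -0.5 points | 0.98 | 5.1% |
| 1.0 | -1.7 points | 0.93 | 6.1% |
| 1.5 | -2.9 points | 0.89 | 8.3% |
| 2.0 | -3.9 points | 0.85 | 11.2% |

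With equal success (20% vs 20%) the bias is zero and rejection is 5.0%. At 10% vs 30%, the outer ends of the stated ranges, the difference is -1.1 to -7.9 points and rejection 5.4% to 30.1%.

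**Direct check.** If EMM only turns failures into successes, a share 0.10/0.85 = 11.8% of SMM failures would have succeeded on EMM and have no counterpart among EMM failures. If they do 10, 20 or 30 points better in Phase 2, the spurious difference is 0.118 × 10, 20 or 30 = 1.2, 2.4 or 3.5 points.

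**When there is no bias.** If the failure probability is g(U) × h(arm), with U the prognosis, the distribution of U among failures is proportional to f(U)g(U) in both arms and h cancels. There is also no bias if U has no bearing on Phase 2 outcome.

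**An alternative that does not work.** One could analyse all Phase 1 subjects with the outcome Phase 1 success or Phase 2 improvement. Entry among failures is 50%/80% = 62.5%. With no carry-over and ρ = 0.5:
- SMM: 0.15 + 0.85 × 0.625 × 0.400 = 36.25%.
- EMM: 0.25 + 0.75 × 0.625 × 0.368 = 42.25%.

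The difference is +6.0 points (+6.7 at ρ = 0.3, +5.2 at ρ = 0.7). With 324 per arm, a 5% test rejects 41%, 35% and 27% of the time at ρ = 0.3, 0.5 and 0.7. It largely re-tests Hypothesis 1.1.

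**The case against.** The strongest reply is that item 7 gives an explicit reading only for the interaction, and attaches no stated conclusion to the Phase 1 arm main effect. A Phase 2 outcome exists only for entrants, and the protocol is open about who they are. The section is exploratory, no primary or secondary hypothesis depends on this term, and interpretive caveats are often left to an analysis plan or publication.

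Most of that stands, and it keeps the point minor. It does not remove it. Once the interaction is dropped, the main effect is the only term left that addresses the question item 7 says it will formally test. A general label of weaker evidence does not tell a reader that this estimate is biased or in which direction. The reading given for the interaction has a similar gap. Each EMM vs SMM effect within a Phase 1 arm is randomised, but the interaction contrasts those effects between two differently selected groups.

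A second reply also stands in part. Phase 1 failure includes missed booster visits, two or more missing urines and outside treatment, so it is not a clean ranking on Phase 2 prognosis. A reader might infer that the two groups must differ in prognosis by construction. The documents do not support that: it needs shared drivers of both outcomes, and the multiplicative case in the working shows that it can fail.

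**Conclusion.** The point holds as one about what item 7 can conclude. Its Phase 1 arm main effect is not a randomised comparison. Under the protocol's own Phase 1 hypothesis, and if prognosis carries over between phases, it is biased towards prior counselling looking harmful. At 15% vs 25% Phase 1 success the bias is about 0.5 to 5 points and the nominal 5% test rejects about 5% to 15% of the time. Both ranges rest on an assumed link between the phases, on entry unrelated to arm given failure, and on ignoring site clustering.

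A reader might go further and infer that the primary Phase 2 comparison is compromised. It is not, because EMM vs SMM is re-randomised within Phase 1 arm.

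**What to change.** - In item 7, replace the sentence promising a formal test. State instead that the main effect, the interaction and the similar analyses of the secondary hypotheses describe associations among Phase 1 failures who entered Phase 2, and do not estimate an effect of Phase 1 assignment.
- Report Phase 1 failure rates, Phase 2 entry rates and entrants' baseline characteristics by Phase 1 arm.
- Add a sensitivity fit adjusted for the baseline predictors already listed in 11.3.2.3. That list is preferable to 11.4.2.3, which includes variables measured after the Phase 1 randomisation, such as time to and reason for failure.
- Do not use the composite of Phase 1 success or Phase 2 improvement as a carry-over test, since it generally differs between arms when Hypothesis 1.1 is true, even without carry-over.

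The cost is a change of wording, a descriptive table and one more exploratory fit on data already collected. Selection on unmeasured prognosis remains after adjustment, and the text should say so.
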